5.1.3 Statistical Methods for Observational Objectives

No hypotheses will be tested. Descriptive statistics will be presented. Safety results will be described for subjects in all study groups. The main parameters for the safety endpoints will be described by 95% CI using the exact binomial method (Clopper-Person method) (1).

5.1.4 Complementary analysis

5.1.4.1 Sensitivity Analysis due to COVID-19 Pandemic

The impact of COVID-19 pandemic situation on study conduction will be summarized through impact on visit procedures, study completion and major/critical protocol deviations due to COVID-19.

The subjects impacted by COVID-19 pandemic situation will be defined as the subjects with at least one major/critical protocol deviation due to COVID-19 or who did not complete the study due to COVID-19. If more than 10% of subjects are impacted as per this definition, baseline and demographics characteristics, and the main immunogenicity and safety endpoints will also be summarized in the subsets of subjects impacted/ non-impacted subjects to assess the potential impact of COVID-19 situation on study outcome.

-
- Confidential/Proprietary Information
 - Page 59 of 67

5.1.4.2 Subgroup analysis

Additional subgroup analyses by gender and race based on PPAS will be provided for primary and main secondary immunogenicity endpoints.

The gender subgroup analyses will have two categories (Female and Male), and the race subgroup analyses will have four categories (White, Black, Asian, and Other).

The following parameters will be assessed 30 days after the last vaccination in the second year and 30 days after the last vaccination in infant series:

- hSBA GMTs with 95% CI
- Percentage of subjects with hSBA titer \geq 1:8 and 95% CI
- Percentage of subjects with hSBA vaccine seroresponse and 95% CI

The safety overview will be also described by race and gender

5.2 Analysis Sets

5.2.1 Per-Protocol Analysis Set

The per-protocol analysis set (PPAS) is a subset of the FAS. Immunogenicity analyses will primarily be performed on the per-protocol analysis sets. There will be 2 PPAS corresponding to the 2 FAS:

- PPAS for infant vaccination (PPAS1)
- PPAS for 2nd year of life vaccination (PPAS2)

5.2.1.1 Per-Protocol Analysis Set 1 (PPAS1)

Serology obtained from the last blood sample of infancy vaccination stage for all antigens will be used for immunogenicity analyses of infant stage of the study.

The subjects presenting with at least one of the following relevant protocol deviations during infancy will be excluded from the PPAS1:

- Subject did not meet all protocol-specified inclusion criteria or met at least one of the protocol-specified exclusion criteria
- Subject did not complete the vaccination schedule
- Subject received a vaccine other than the one that he / she was randomized to receive

- Preparation and / or administration of vaccine was not done as per-protocol
- Subject did not receive vaccine in the proper time window, according to the Tables of Study Procedures. All infant stage vaccines (including concomitant vaccines) need to be received as scheduled in the Table of Study Procedures.
- Subject did not provide post-dose serology sample during infancy in the proper time window or a post-dose serology sample was not drawn
- Subject received a protocol-prohibited therapy, medication or vaccine

In addition to the reasons listed above, subjects will also be excluded from the PPAS1 if their infancy post vaccination serology sample did not produce a valid test result (ie, results for all antigens are missing).

In the event of a local or NIC with a pandemic influenza or coronavirus vaccine or any other vaccine as needed, subjects who receive 1 or more doses of the pandemic influenza or coronavirus vaccine at any time during the study will not be withdrawn from the study.

5.2.1.2 Per-Protocol Analysis Set 2 (PPAS2)

Serology obtained from the last blood sample of 2nd year of life for all antigens will be used for immunogenicity analyses of 2nd year of the study.

The subjects presenting with at least one of the following relevant protocol deviations during 2nd year of life will be excluded from the PPAS2:

- Subject did not meet all protocol-specified inclusion criteria or met at least one of the protocol-specified exclusion criteria
- Subject did not complete the vaccination schedule including the infant and the 2nd year of the study
- Subject received a vaccine other than the one that he / she was randomized to receive during both the infant and 2nd year of the study
- Preparation and / or administration of vaccine was not done as per-protocol during both the infant and 2nd year of the study
- Subject did not receive vaccine in the proper time window. All 2nd year of life vaccines (including concomitant vaccines) need to be received as scheduled in the Table of Study Procedures.
- Subject did not provide post-dose serology sample during infancy in the proper time window or a post-dose serology sample was not drawn during 2nd year of life

- Subject received a protocol-prohibited therapy, medication or vaccine

In addition to the reasons listed above, subjects will also be excluded from the PPAS2 if their 2nd year of life post vaccination serology sample did not produce a valid test result (ie, results for all antigens are missing).

In the event of a local or NIC recommendation or requirement with a pandemic influenza or coronavirus vaccine or any other vaccine as needed, subjects who receive 1 or more doses of the pandemic influenza or coronavirus vaccine at any time during the study will not be withdrawn from the study.

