5.2.2 Full Analysis Set

There will be 2 full analysis sets (FAS) for this study:

- FAS for infant vaccination (FAS1). The full analysis set 1 (FAS1) is defined as the subset of all randomized subjects who received at least 1 dose of the study vaccine in infancy (<12 months of age) and have a valid post-vaccination serology result in infancy. All subjects will be analyzed according to the treatment group to which they were randomized.
- FAS for 2nd year of life vaccination (FAS2). The full analysis set 2 (FAS2) is defined as the subset of all randomized subjects who received at least 1 dose of the study vaccine in the 2nd year of life (≥ 12 months of age) and have a valid post-vaccination serology result in the 2nd year of life. All subjects will be analyzed according to the treatment group to which they were randomized.

Immunogenicity analyses will be performed on the FAS for exploratory purposes.

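### The per-protocol set behind the primary endpoint (PPAS2) puts the sampling window on the infancy sample and none on the second-year sample it analyses

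*SAP*

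**What the plan says.** SAP 4.1.1.1 sets the primary endpoints at 30 days after the last second-year vaccination, for Groups 1 and 2 in Mexico and Group 3 in the Russian Federation. SAP 5.2.4 runs all immunogenicity analyses on PPAS1 and PPAS2. For PPAS2, SAP 5.2.1.2 says: "Serology obtained from the last blood sample of 2nd year of life for all antigens will be used". That sample is BL0003, taken at Visit 6 in Mexico and Visit 7 in the Russian Federation. SAP 3.1 schedules it 30 days (+14) after the 12-month dose.

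The PPAS2 exclusion list opens by saying that subjects with "relevant protocol deviations during 2nd year of life will be excluded from the PPAS2". Its serology bullet then removes a subject who did not provide a post-dose sample "during infancy in the proper time window or a post-dose serology sample was not drawn during 2nd year of life". Protocol 12.2.5 uses the same words.

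**The concern.** The window is attached to the wrong sample. PPAS2 analyses BL0003, yet its only sample-timing condition concerns the infancy sample, BL0002. Followed as written, the rule has two effects:

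- A BL0003 drawn before day 30 or after day 44 remains in the per-protocol set and counts towards an endpoint defined at 30 days.
- A subject whose BL0003 was on time is excluded if the infancy sample was late or early.

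The primary percentages for Groups 1, 2 and 3 depend on this set, as do all other second-year results reported on it. One programmer could apply the literal text and another the apparent intent, and they would build different primary populations. A prespecified analysis set is meant to prevent that.

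**Working it through.** **Comparison of the two per-protocol definitions (SAP 5.2.1.1 and 5.2.1.2)**

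| Rule | PPAS1 | PPAS2 |
|---|---|---|
| Sample analysed | Last infancy sample (BL0002) | Last second-year sample (BL0003) |
| Vaccine timing | "All infant stage vaccines (including concomitant vaccines) need to be received as scheduled" | "All 2nd year of life vaccines (including concomitant vaccines) need to be received as scheduled in the Table of Study Procedures" |
| Sample timing | "Subject did not provide post-dose serology sample during infancy in the proper time window" | Same infancy phrase kept; no window for BL0003 |
| Sample not drawn | Infancy sample | Second-year sample |

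In PPAS1 the window applies to the sample being analysed. Between PPAS1 and PPAS2 the vaccine bullet was updated to the second year, but the timing half of the serology bullet was not. This looks like a carry-over.

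**Search for another rule that times BL0003**

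- The PPAS2 vaccine-window bullet covers vaccines, not blood samples.
- The closing PPAS2 sentence asks only for a valid test result.
- FAS2 (SAP 5.2.2) requires subjects to have been vaccinated in the second year "and have a valid post-vaccination serology result in the 2nd year of life", with no timing.
- SAP 5.7 corrects the measles cutoff but not this bullet.

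No sentence names PPAS2 for the primary endpoint. That link is inferred from the endpoint timing, the sample PPAS2 uses and SAP 5.2.4; no other set fits.

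**Effect of keeping off-window samples.** The plan gives no figure on this point. Its only sample-size figures concern adverse-event detection and do not bear on it. The change in a percentage is an identity:

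change = f × (off-window rate − in-window rate)

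Here f is the off-window share. Assumptions: f from 2% to 15%; in-window rate 95%, within the 91% to 100% that protocol 1.2.1.1 reports for MET39 after the second-year dose; difference from -10 to +5 points, where +5 is the ceiling at 95%. Changes in percentage points:

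| f | -10 | -5 | 0 | +5 |
|---|---|---|---|---|
| 2% | -0.20 | -0.10 | 0 | +0.10 |
| 5% | -0.50 | -0.25 | 0 | +0.25 |
| 10% | -1.00 | -0.50 | 0 | +0.50 |
| 15% | -1.50 | -0.75 | 0 | +0.75 |

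**Scale.** The Clopper-Pearson 95% limits are the 2.5% quantile of Beta(x, n−x+1) and the 97.5% quantile of Beta(x+1, n−x). With x = 0.95n at planned enrolment, the widths are 6.58 points (n=200), 7.70 (n=150) and 9.64 (n=100). Half of each is 3.3, 3.9 and 4.8 points. The n=150 figure uses x = 142.5, so it is an interpolation.

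**Effect of wrongly excluding subjects for the infancy sample.** Assume 0% to 20% are removed and the response rate stays at about 95%:

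- Group 1: 190/200 gives 91.0% to 97.6%; 152/160 gives 90.4% to 97.8%.
- Group 2: 95/100 gives 88.7% to 98.4%; 76/80 gives 87.7% to 98.6%.
- Group 3: 142/150 gives 89.8% to 97.7%; 114/120 gives 89.4% to 98.1%.

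Precision changes little. What changes is which subjects and which sample times enter the estimate.

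**The case against.** **The intent can be inferred.** The list stem speaks of the second year, the set uses the second-year sample, the schedule gives BL0003 a window and PPAS1 shows the pattern. A programmer may well apply the intended rule. This is fair, but it is an argument for correcting the text. The infancy clause could also be deliberate, because another PPAS2 bullet reaches back by excluding a subject who "did not complete the vaccination schedule including the infant and the 2nd year of the study". Even then BL0003 has no window.

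**Other safeguards exist.** The blind data review (SAP 5.6) could find mistimed samples, and COVID-related effects on visits and major deviations are summarised (SAP 5.1.4.1). Protocol 5.2.10 lists non-compliance with time windows as significant, but it classifies reasons for early termination, so it says little about a sample taken at the final visit. None of these links a mistimed BL0003 to exclusion from PPAS2.

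**The effect is small and the inputs are weak.** This stands. Nothing is tested, the share and the difference are assumptions, and MET39 gave only MenACYW in US subjects on several schedules, so it offers no basis for the Menveo group. Actual PPAS2 groups may be smaller than planned enrolment, with wider intervals. The case for a change rests on the rule for the primary set being wrong as written, not on a demonstrated bias.

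**Conclusion.** The concern holds. Both documents define the per-protocol set for the primary endpoint with a timing rule on the wrong sample, and nothing else in the plan repairs it. The gap lies in the analysis-set rule: the visit schedule does set a window for BL0003, but it is not an exclusion criterion.

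The size and direction of any effect cannot be determined from the documents. Under the stated assumptions the primary percentage moves by -1.5 to +0.75 points, by -0.2 to +0.1 at a 2% share, and not at all if off-window responses do not differ. Throughout that range the shift is below sampling error. Confidence is high in the wording gap, not in any numerical effect. It should be fixed because it concerns the primary set and the correction is simple.

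**What to change.** Amend the serology bullet in SAP 5.2.1.2 and protocol 12.2.5, or record the correction in SAP 5.7 as was done for the measles cutoff. Suggested wording: *Subject did not provide the post-dose serology sample in the 2nd year of life (BL0003) in the proper time window, or this sample was not drawn.* State separately whether a mistimed BL0002 also excludes a subject from PPAS2, and align the list stem with that decision. Reporting the number of BL0003 samples before day 30 and after day 44, by group, would be a useful addition.

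This should be settled before the first database lock. SAP 5.7 makes the data in the first analysis final and defers only PRP and rSBA, so hSBA is fixed at that point. The documents do not say whether that lock has already passed.

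The cost is one bullet per document or one SAP entry, using dates already collected, and some loss of precision if samples leave the set. If 2% to 15% leave (assumption) and the rate is 95%, the exact CI width rises from 6.6 to 6.7–7.2 points for n=200, from 7.7 to 7.8–8.4 for n=150, and from 9.6 to 9.8–10.6 for n=100. Most of these widths use fractional counts and are interpolations.

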5.2.2 Full Analysis Set

There will be 2 full analysis sets (FAS) for this study:

- FAS for infant vaccination (FAS1). The full analysis set 1 (FAS1) is defined as the subset of all randomized subjects who received at least 1 dose of the study vaccine in infancy (<12 months of age) and have a valid post-vaccination serology result in infancy. All subjects will be analyzed according to the treatment group to which they were randomized.
- FAS for 2nd year of life vaccination (FAS2). The full analysis set 2 (FAS2) is defined as the subset of all randomized subjects who received at least 1 dose of the study vaccine in the 2nd year of life (≥ 12 months of age) and have a valid post-vaccination serology result in the 2nd year of life. All subjects will be analyzed according to the treatment group to which they were randomized.

Immunogenicity analyses will be performed on the FAS for exploratory purposes.

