**Table 5.3: Schedule of antigen testing: Mexico (Groups 1 and 2)**

Visit (V)	V01	V02	V03	V04	V05	V06
Subject Age	2 months	4 months	6 months	7 months	12 months	13 months
Trial Timeline	D0	V01 + 60 days	V02 + 60 days	V03 + 30 days	V04 + 150 to 180 days	V05 + 30 days
BL (5 mL)	BL0001			BL0002		BL0003
Group 1	Meningococcal Serogroups (A, C, Y, W)* Pertussis (PT, FHA) RV IgA	—	—	Meningococcal Serogroups (A, C, Y, W) PCV13 RV IgA		Meningococcal Serogroups (A, C, Y, W) PCV13 Hib (PRP) Pertussis (PT, FHA) HepB Polio (types 1, 2, 3) Tetanus Diphtheria M-M-R®II

Group 2
	
Meningococcal Serogroups (A, C, Y, W) Pertussis (PT, FHA) RV IgA
	
—
	
—
	
Meningococcal Serogroups (A, C, Y, W) PCV13 RV IgA
		
Meningococcal Serogroups (A, C, Y, W) PCV13 Hib (PRP) Pertussis (PT, FHA) HepB Polio (types 1, 2, 3) Tetanus Diphtheria M-M-R®II

-----------------------	---	----------	----------	---	--	--

PT: pertussis toxin; FHA: filamentous hemagglutinin; Hib: *Haemophilus influenzae* type B; PRP: polyribosyl-ribitol phosphate; HepB: hepatitis B; PCV13: pneumococcal 13-valent conjugate vaccine; M-M-R®II: measles, mumps, and rubella

\*Antibody responses to meningococcal serogroups (A, C, Y, and W) will be measured by rSBA before the first vaccination (Visit 1), 30 days after the final vaccination in the infant series, and 30 days after the last vaccination in the entire 3- or 4- dose vaccine schedule in a subset of subjects (100 subjects per group in Groups 1, 3, and 5 and 50 subjects per group in Groups 2, 4, and 6.)

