- 15) Remind the parent / guardian to notify the site in case of an SAE.
- 16) Complete the CRFs for this visit.

---

a Failure to administer vaccines in the designated limb will not constitute a protocol deviation, but should be recorded as a comment in the CRF. If the initial vaccines are administered in the wrong limbs, this should be corrected for subsequent injections.

b The only other vaccine that can be administered with the meningococcal vaccine in the right thigh is ENGERIX-B®. Do not administer Pentaxim® or PREVNAR 13® in the right thigh.

c Multiple injections given in the same extremity should be separated as far as possible preferably 2.54 cm to 3.81 cm apart with a minimum of 2.54 cm. Keep the subject under observation for 30 minutes and record any AR in the source document.

Telephone Call 1 (8 [+2] days after Visit 1)

**Note:** If Day 8 falls on a weekend or a holiday, the telephone call may be made on the following business day.

- 1) Record relevant information concerning the subject's health status on the telephone contact form. If an SAE has occurred that has not yet been reported, follow the instructions in [Section 10](#) for reporting it.
- 2) Remind the parent / guardian to do the following:
  - Complete the D0 to D07 pages of the diary card.
  - Complete the remaining pages of the diary card, and bring them to the next visit.
  - Notify the site in case of an SAE.

Visit 2 (60 [+14] days after Visit 1): Collection of Safety Information and Vaccination

- 1) If the diary card information from D0 to D07 (DC1) has not yet been obtained, obtain it at this time. Collect and review the pages of the diary card with the parent / guardian, including any AEs, medications, or therapy that occurred since vaccination. If an SAE, including an AESI, has occurred, follow the instructions in [Section 10](#) for reporting it.
- 2) Review warnings and precautions to vaccinations.
- 3) Review contraindications to subsequent vaccinations.
- 4) Review conditions for withdrawal.
- 5) Contact IRT system for dose number for all vaccines to be given.
- 6) Administer the appropriate study vaccine per Operating Guidelines. Each vaccine should be administered in an assigned location and documented appropriately.

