***For subjects in Groups 1 and 2:***

- Prevnar 13®: inject IM into the anterolateral area of the thigh (preferably the left thigh).

---

a The only other vaccine that can be administered with the meningococcal vaccine in the right thigh is ENGERIX-B®. Do not administer Pentaxim® or PREVNAR 13® in the right thigh.

b Multiple injections given in the same extremity should be separated as far as possible preferably 2.54 cm to 3.81 cm apart with a minimum of 2.54 cm. Keep the subject under observation for 30 minutes and record any adverse reaction (AR) in the source document.

- Hexacima®: inject IM into the anterolateral area of the thigh (preferably the left thigh).b
  - RotaTeq®: administer PO per instructions in the package insert.
- 7) Give the parent / guardian a diary card (DC2).
  - 8) Remind the parent / guardian to expect a telephone call 8 days after Visit 2 and to bring back the diary card when they return for Visit 3 at a specified date and time.
  - 9) Remind the parent / guardian to notify the site in case of an SAE.
  - 10) Complete the relevant CRFs for this visit.

Telephone Call 2 (Group 2) (8 [+2] days after Visit 2)

Refer to steps in Telephone Call 1.

Visit 3 (60 [+14] days after Visit 2): Collection of Safety Information and Vaccination

- 1) If the diary card information from D0 to D07 (DC2) has not yet been obtained, obtain it at this time. Collect and review the pages of the diary card with the parent / guardian, including any AEs, medications, or therapy that occurred since vaccination. If an SAE, including an AESI, has occurred, follow the instructions in [Section 10](#) for reporting it.
- 2) Review warnings and precautions to vaccinations.
- 3) Review contraindications to subsequent vaccinations.
- 4) Review conditions for withdrawal.
- 5) Contact IRT system for dose number for all vaccines to be given.
- 6) Administer the appropriate study vaccine per Operating Guidelines. Each vaccine should be administered in an assigned location and documented appropriately.
  - Meningococcal vaccine: inject IM into the anterolateral area of the thigh (preferably the right thigh).a,b
  - Hexacima®: inject IM into the anterolateral area of the thigh (preferably the left thigh).
  - Prevnar 13®: inject IM into the anterolateral area of the thigh (preferably the left thigh).b

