  - RotaTeq®: administer PO per instructions in the package insert.

---

a The only other vaccine that can be administered with the meningococcal vaccine in the right thigh is ENGERIX-B®. Do not administer Pentaxim® or PREVNAR-13® in the right thigh.

b Multiple injections given in the same extremity should be separated as far as possible preferably 2.54 cm to 3.81 cm apart with a minimum of 2.54 cm. Keep the subject under observation for 30 minutes and record any AR in the source document.

- 7) Keep the subject under observation for 30 minutes and record any AE in the source document.
- 8) Give the parent / guardian a diary card (DC3).
- 9) Remind the parent / guardian to expect a telephone call 8 days after Visit 3 and to bring back the diary card when they return for Visit 4 at a specified date and time.
- 10) Remind the parent / guardian to notify the site in case of an SAE.
- 11) Complete the relevant CRFs for this visit.

Telephone Call 2 (Group 1) (8 [+2] days after Visit 3) / Telephone Call 3 (Group 2) (8 [+2] days after Visit 3)

Refer to steps in Telephone Call 1.

Visit 4 (30 [+14] days after Visit 3): Collection of Safety Information and Blood Sampling

- 1) If the diary card information from D0 to D07 (DC3) has not yet been obtained, obtain it at this time. Collect and review the pages of the diary card with the parent / guardian, including any AEs, medications, or therapy that occurred since vaccination. If an SAE, including an AESI, has occurred, follow the instructions in [Section 10](#) for reporting it.
- 2) Review temporary contraindications to blood sampling
- 3) Collect 6-mL blood sample (BL0002) (see [Section 7.1](#) for detailed instructions regarding the handling of blood samples).
- 4) Give the parent / guardian a diary card (DC4).
- 5) Remind the parent / guardian to bring back the diary card when they return for Visit 5 at a specified date and time.
- 6) Remind the parent / guardian to notify the site in case of an SAE.
- 7) Complete the relevant CRFs for this visit.

Telephone Call 3 (Group 1) (14 [+ 2] days before Visit 5) / Telephone Call 4 (Group 2) (14 [+ 2] days before Visit 5)

- 1) Contact the subjects' parent/ guardian by telephone within 14 days before V05 to remind them about the forthcoming study visit.
- 2) If the subject participation in the study is discontinued:

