  - a. Review the diary card including any AEs, medications, or therapy that occurred since the last visit.
  - b. Ask the subject's parent / guardian if the subject has experienced any SAE in the time since vaccination that has not been reported to the study personnel. If an SAE, including an AESI, has occurred, follow the instructions in [Section 10](#) for reporting it.
  - c. Make arrangements to retrieve the diary card.

Visit 5 (5 months [+14 days] after Visit 4): Collection of Safety Information and Vaccination

- 1) If the diary card information from D0 to D07 (DC4) has not yet been obtained, obtain it at this time. Collect and review the pages of the diary card with the parent / guardian, including any AEs, medications, or therapy that occurred since vaccination. If an SAE, including an AESI, has occurred, follow the instructions in [Section 10](#) for reporting it.
- 2) Review the subject's relevant health history with parent / guardian, including any AEs, medications, or therapy that occurred since vaccination.
- 3) Review warnings and precautions to vaccinations.
- 4) Review contraindications to subsequent vaccinations.
- 5) Review conditions for withdrawal.
- 6) Contact IRT system for dose number for all vaccines to be given.
- 7) Administer the appropriate study vaccine per Operating Guidelines. Each vaccine should be administered in an assigned location and documented appropriately:
  - Meningococcal vaccine: inject IM into the anterolateral area of the thigh (preferably the right thigh).a,b
  - Prevnar 13®: inject IM into the anterolateral thigh (preferably the left thigh).a
  - M-M-R®II inject SC into the outer aspect of the upper arm (preferably the left arm)
  - Hexacima®: inject IM into the anterolateral area of the upper thigh (preferably the left thigh)
- 8) Keep the subject under observation for 30 minutes and record any AE in the source document.
- 9) Give the parent / guardian a diary card (DC5).
- 10) Remind the parent / guardian to expect a telephone call 8 days after Visit 5 and to bring back the diary card when they return for Visit 6 at a specified date and time.
- 11) Remind the parent / guardian to notify the site in case of an SAE.
- 12) Complete the relevant CRFs for this visit.

---

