#### 5.2.4 Inclusion Criteria

An individual must fulfill *all* of the following criteria to be eligible for study enrollment:

- 1) Infants 2 months of age (60 to 89 days of age) on the day of the first study visit.a
- 2) Born after a full-term pregnancy with an estimated gestation age  $\geq 37$  weeks and a birth weight  $\geq 2.5$  kg
- 3) Informed consent form has been signed and dated by the parent(s) or guardian(s), as required by local regulationsb
- 4) Subject and parent/guardian are able to attend all scheduled visits and to comply with all trial procedures
- 5) In good health as determined by medical history and physical assessment.

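### The second-year full analysis set tests age at dosing, but the visit intervals allow an on-schedule 12-month dose on day 360 to 363, so read literally a few compliant children leave the primary analysis

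*SAP*

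**What the plan says.** FAS2 is the "subset of all randomized subjects who received at least 1 dose of the study vaccine in the 2nd year of life", with that phrase glossed as 12 months of age or more, plus a valid second-year serology result (SAP 5.2.2; same rule in protocol 12.2.1). FAS1 uses the complementary condition, under 12 months.

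SAP 5.2.1 adds that "The per-protocol analysis set (PPAS) is a subset of the FAS". SAP 5.2.4 runs all immunogenicity analyses primarily on the per-protocol sets. The primary endpoint is hSBA of at least 1:8, 30 days after the second-year dose (SAP 4.1.1.1). PPAS2 therefore inherits the age condition. Its own timing rule (SAP 5.2.1.2) refers to the Table of Study Procedures, which gives age only as approximate.

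Eligibility is "Infants 2 months of age (60 to 89 days of age) on the day of the first study visit" (protocol 5.2.4). For Mexico, protocol 5.1.4 sets "Visit 2 (60 [+14] days after Visit 1"), "Visit 3 (60 [+14] days after Visit 2"), "Visit 4 (30 [+14] days after Visit 3") and "Visit 5 (5 months [+14 days] after Visit 4"). Table 5.3 gives the last interval as "V04 + 150 to 180 days". No minimum age is attached to the 12-month visit.

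SafAS6 (SAP 5.2.3.7) identifies the same dose as the one given at Visit 5 in Mexico or Visit 6 in Russia, with age stated loosely.

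**The concern.** Two clocks are in use. Membership of FAS2 depends on age at dosing, while compliance depends on the interval since the previous visit. Nothing ties them together at 12 months. A child can satisfy every visit window, and so the PPAS2 timing rule, and still receive the dose shortly before the first birthday. The literal rule then removes that child from the primary analysis for having been enrolled young and seen punctually, which has no scientific purpose.

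The same dose counts for safety in SafAS6 but not for immunogenicity in FAS2. If the age condition is not meant literally, neither document says so, and the choice falls to whoever programs the analysis sets in an open-label trial.

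**Working it through.** **Inputs.** Enrolment age 60 to 89 days (protocol 5.2.4). Minimum intervals from protocol 5.1.4: Mexico 60, 60 and 30 days, then 5 months; Russia 30, 45, 45 and 30 days, then 5 months. All windows are plus-only (+14 days). Five calendar months are 150 to 153 days. In Russia, Visit 1 may fall 0 to 5 days after Visit 0 (protocol 5.1.1).

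**The plan's own figure.** With no delay, over all enrolment ages and all dates in the planned inclusion period (18 October 2018 to 18 December 2020), the dose falls on day 360 to 392. This agrees with the tabulated approximate age of 12 months.

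**Earliest compliant dose.**
- Mexico: 60 + 60 + 60 + 30 + (150 to 153) = 360 to 363 days.
- Russia, Visit 0 and Visit 1 on the same day: 60 + 30 + 45 + 45 + 30 + (150 to 153) = 360 to 363 days.
- Russia, Visit 1 one day later: 361 to 364 days. Five days later: 365 to 368 days, and no child is affected.

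The first birthday is day 365 or 366. Calendar enumeration puts the dose 2 to 5 days early for enrolment on day 60.

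**Worked case.** Born 1 January 2019; enrolled 2 March (day 60); Visit 2 on 1 May; Visit 3 on 30 June; Visit 4 on 30 July; Visit 5 on 30 December 2019. Age at dose is 363 days, two days before the birthday, with every visit on schedule.

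**Who is exposed.** With no delay at all in Mexico, the share dosed before the birthday by enrolment age is 100% at 60 and 61 days, 65% at 62, 38% at 63, 7% at 64, and none later. Over uniform ages 60 to 89 that is about 10.4%.

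**Share affected.** The documents give no attendance data, so every pattern below is an assumption. First set: simulated on calendar dates, with the Russian Visit 0 to Visit 1 gap uniform over 0 to 5 days.

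| Enrolment age (days) | Delay at each visit | Mexico | Russia |
|---|---|---|---|
| uniform 60-89 | uniform 0-14 days | 0.01% | 0.0% |
| uniform 60-89 | uniform 0-3 days | 0.45% | 0.03% |
| uniform 60-89 | 60% none, otherwise 1-7 days | 2.1% | 0.4% |
| uniform 60-89 | none | 10.7% | 3.7% |
| uniform 60-66 | 60% none, otherwise 1-7 days | 8.6% | 1.7% |
| uniform 60-66 | none | 44.5% | 16.3% |

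The no-delay rows are limiting cases. The 10.7% is a simulation estimate of the enumerated 10.4%.

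Second set: skewed attendance. Enrolment averages 5 or 8 days after day 60, and each of Mexico's four later visits averages 1 to 2 days late. The slack is 365 - (60 + 60 + 60 + 30 + 152) = 3 days, or 2 days if the five months are 153 days. A child is affected when enrolment excess plus all delays is below the slack. The lower figure in each cell uses exponential delays; the higher uses geometric whole-day delays.

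| Mean excess / mean visit delay | 152 days | 153 days |
|---|---|---|
| 5 / 1 day | 5.6-9.1% | 1.4-4.0% |
| 5 / 2 days | 0.9-2.4% | 0.2-0.9% |
| 8 / 1.5 days | 1.3-3.1% | 0.3-1.2% |

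Hand check of the largest cell (geometric, 5 / 1 day, slack 3): P(total 0) = (1/6)(1/2)^4 = 1/96 = 1.04%. P(total 1) = (1/96)(5/6 + 4 x 1/2) = 2.95%. P(total 2) = (1/96)(25/36 + (5/6)(2) + 10/4) = 5.06%. The sum is about 9.1%.

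Russia has five later visits. The same patterns, even with no Visit 0 to Visit 1 gap, run from a few hundredths of a percent to just under 6%; a gap lowers them further.

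**The case against.** The best counter-argument is that second year of life is a stage label here. The reminder call is scheduled before the first visit of that stage, PPAS2 speaks of the second year of the study, and SafAS6 works by visit. A programmer would probably assign FAS2 by visit. That is plausible, but FAS2 adds an explicit age gloss and nothing says to ignore it.

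Next, the only month-to-day conversion in the documents equates 2 months with 60 to 89 days. On 30-day months, 12 months is 360 days and nobody fails the numerical condition. The same footnote also defines 2 months by calendar month, no day count is given for 12 months, and day 360 to 363 is still before the first birthday and so not in the second year of life. This leaves an ambiguity, not an answer.

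It is also fair that the protocol schedules the dose at 12 months of age and that the +14-day window lets a site satisfy both interval and birthday. It does not oblige a site to do so.

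Some stronger readings should be resisted. A reader might infer from the plus-only windows that sites aim for the earliest day; no passage says this. A reader might put the loss near 20%. Under the skewed patterns above, that arises only if fractional delays are rounded down, which turns a nominal mean delay of 1 day into about 0.58. A reader might take Russia to be equally exposed; only its earliest possible age matches Mexico's. A reader might expect FAS1 to be wrong too, but an affected child already has earlier infant doses, so FAS1 membership does not turn on this dose.

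**Conclusion.** The conflict is in the text and holds under one stated assumption, that 12 months means the first birthday. FAS2, and through it PPAS2 and the primary analysis, can then exclude children who kept every visit window, while SafAS6 retains the same dose.

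It is an edge case, confined to enrolment at about 60 to 64 days with almost no accumulated delay. The expected share is about 0.01% or less with uniform ages and delays over the full windows, and roughly 0.2% to 9% in Mexico under the assumed skewed attendance. Of the 300 children planned there, 0.2% is fewer than one child and 9% is 27. Russia would lose a smaller share. Higher figures require every visit to fall on its first permitted day.

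A reader might infer a biased comparison of MenACYW with Menveo. The documents do not support that: Groups 1 and 2 share one visit schedule and one age rule, and no hypothesis is tested. The harm is a needless, age-selective loss and an ambiguously defined primary population. This is a minor point, worth correcting because the correction is nearly free.

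**What to change.** Define FAS2 by visit and sample: randomised subjects who received study vaccine at Visit 5 (Mexico) or Visit 6 (Russia) and have a valid BL0003 result. Drop the age condition. Off-schedule doses are already handled by the PPAS2 timing rule. Add one sentence stating that second year of life, wherever it appears in the endpoints and analysis sets, denotes the dose at that visit.

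A parallel FAS1 wording (at least one dose at an earlier visit and a valid BL0002 result) is for consistency only and changes no one's membership.

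Separately, the Mexican Visit 4 to Visit 5 interval is 5 months plus up to 14 days in the procedures but 150 to 180 days in Table 5.3; those passages must be reconciled.

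The cost is a few lines in SAP 5.2.2 and an entry in SAP 5.7, which already records a correction to the protocol's measles cutoff. Trial conduct and data collection do not change. The wording should be settled before the analysis sets are programmed.
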